11.1.6 Assessment of Mortality Through the 12-month Post-RT Clinic Visit

All deaths through the 12-month follow-up visit will be collected. The number of deaths in each group will be compared using a standard chi-squared analysis. The number of deaths over time will be compared using a Kaplan-Meier survival curve and the survival curves compared using a log-rank test.

11.1.7 **Progression-free Survival**

The duration of progression free survival will be calculated from the date of randomization to the earliest date of the following:

Original: 11 January 2017

Page 53 of 67

- The patient died
- The patient had an imaging report of tumor progression (RECIST 1.1 evaluation of less than "Complete Response")
- The patient completed their 12 month follow-up assessment.

Patients lost-to-follow-up will be censored at the time of their last assessment.

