5.3. Safety Objectives

Safety objectives will include the following:

- To assess the impact that SGX942 has on the Adverse Events (AE) and serious Adverse Events (SAE)
- To assess the impact that SGX942 has on changes in safety laboratory values
- To assess the impact that SGX942 has on the Response Evaluation Criteria in Solid Tumors (RECIST) categorization of the primary tumor at 12 weeks and 12 months CRT
- To assess the impact of SGX942 on the incidence of reported presumed bacterial
 infections between Baseline and 6 weeks after completion of radiation therapy (RT) by
 total number and by severity of infection, graded using the National Cancer Institute's
 (NCI's) Common Terminology Criteria for Adverse Events (CTCAE)
- To assess the impact of SGX942 on 12 month all-cause mortality
- To assess the impact of SGX942 on progression free survival through 12 months

Amendment 2: 22 January 2018 Amendment 3: 17 September 2019

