6.2.1 Oral Mucositis (OM) Grading

OM will be evaluated by personnel trained in the use of the WHO Oral Mucositis Grading system which includes both physical and functional information. This grading system is widely utilized in OM clinical research trials including the Phase 2 trial and is shown in Table 8.

Score	Findings		
0	No findings OR Pain or erythema (not both)		
1	Pain and erythema AND No ulcer		
2	Ulcer and/or pseudomembrane, AND Able to eat solid food AND Able to drink		
3	Ulcer and/or pseudomembrane, AND Not able to eat solid food AND Able to drink		
4	Ulcer and/or pseudomembrane, AND Not able to eat solid food AND Not able to drink		

Table 8: WHO Oral Mucositis Grading System

Only medical personnel at the site who have undergone training and certification in using the WHO Grading system will perform the OM assessments.

6.2.2 **Tumor Status**

The tumor response to treatment will be used as a safety endpoint. Results at 12 weeks and 12 months post-RT will be compared to the Screening results using the RECIST 1.1 system. The evaluation criteria for the target lesion (the primary head and neck carcinoma) are shown in Table 9; the criteria for non-target lesions are shown in Table 10; and the criteria for overall categorization of the tumor status are shown in Table 11. In addition, details pertaining to recurrence of disease, additional therapy, or surgery required after the active treatment phase of the trial is completed will be collected and recorded in the eCRF throughout all follow up visits until 12 months following the last RT treatment.

Confidential

Original: 11 January 2017 Amendment 1: 29 November 2017

Amendment 2: 22 January 2018 Amendment 3: 17 September 2019

Table 9: RECIST Evaluation of the Target Lesion

Target Lesion Response	Measurement	
Complete Response (CR)	All target lesions gone	
Partial Response (PR)	>30% decrease from baseline	
Progressive Disease	>20% increase from smallest sum of longest diameter recorded since treatment started (best response)	
Stable Disease (SD)	Neither Progressive Disease nor Partial Response	

Table 10: RECIST Evaluation of the Non-target Lesion

Target Lesion Response	Measurement	
Complete Response (CR)	All non-target lesions gone Tumor markers gone	
Stable Disease (SD)	Persistence of ≥1 non-target lesion Tumor marker level elevated	
Progressive Disease	Enlargement of non-target lesions	

Table 11: Overall RECIST Response

Target Lesions	Non-target Lesions	New Lesions	Overall Response

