6.3.10 Monthly (2- to 11-Month Post-RT) Follow-up Contacts

All patients will be contacted at least once per month (±2 weeks) through 11 months (except for the 12 week/3 month follow-up visit) following completion of their last RT treatment through

Original: 11 January 2017 Confidential Page 39 of 67

either clinic visits or telephone contacts. For each contact, the following information that will be entered into the eCRF:

- Vital status
- Evidence of recurrence of the primary tumor
- Initiation of additional anti-cancer therapy

6.3.11 12 weeks (3-Month) Post-RT Follow-up Visit

Patients will have a clinic visit at 12 weeks (± 3 weeks) and the following will be performed:

- Interim Medical History
- History of pain and opioid use
- Repeat of the same scans used at the initial tumor staging to be used in a RECIST 1.1 comparison
- Record of tumor status including evidence of tumor recurrence and additional anti-cancer therapies

6.3.12 **12 Month Post-RT Follow-up Visit**

Patients have their last study visit at 12 months (± 28 days) post-RT and the following will be performed:

- Interim Medical History
- History of pain and opioid use
- Evaluation of tumor status
- Repeat of the same scans used at the initial tumor staging to be used in a RECIST 1.1 comparison

Amendment 2: 22 January 2018 Amendment 3: 17 September 2019

Page 41 of 67

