11.1.4 Assessment of Tumor Progression at 12 weeks and 12-months Post-RT

Scans at 12 weeks and 12-months post-RT will be compared to the initial images using the RECIST 1.1 system as outlined in Table 9, Table 10, and Table 11. The percent of the patients categorized as having a "complete tumor response" at 12 weeks and 12 months post-RT will be compared between the treatment groups. Additionally, the percent of the patients categorized as having a "complete tumor response" or "partial tumor response" at 12 weeks and 12 months post-RT will be compared between the treatment groups.

11.1.5 **Infections**

Patients will be assessed at each clinical visit through the 6-week post-RT visit as to the presence of probable clinical infections. All clinical diagnoses of infections will be classified as presumed fungal, presumed viral, or presumed bacterial. The severity of each infection will be graded using the CTCAE (Appendix 1). The incidence of all reported infections, the number of patients with reported infections, the number of presumed fungal, the number of presumed viral and the number of presumed bacterial infections will be compared between treatment groups. The incidence of each type of infection (fungal, viral, and bacterial) by severity grade (1-5) will be displayed.

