12. STATISTICS

12.1. Overview

Complete details of analyses and relative order of importance of each analysis are more fully delineated in the Statistical Analysis Plan.

Given the anticipated non-Gaussian distribution of values for duration of OM, the severity-weighted OM calculations (AUC), and the days to onset of OM, treatment groups will be compared for these variables using a log-rank test of the differences in the duration of SOM between the SGX942 and placebo treated groups. The incidence of OM, percent of RECIST complete responders, and percent of patients with each category of infection will be compared using chi-squared tests. The primary analysis population will be patients who have received enough radiation exposure to put them at significant risk of developing SOM (defined as a cumulative radiation dose of at least 55 Gy).

Original: 11 January 2017 Amendment 1: 29 November 2017

Amendment 2: 22 January 2018 Amendment 3: 17 September 2019

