#### 2.4.2 Tumor Status

The tumor response to treatment will be used as a safety endpoint. Results at 12 weeks and 12 months post-RT will be compared to the Screening results using the RECIST 1.1 system. The evaluation criteria for the target lesion (the primary head and neck carcinoma) are shown in Table 3; the criteria for non-target lesions are shown in Table 4; and the criteria for overall categorization of the tumor status are shown in Table 5. In addition, details pertaining to recurrence of disease, additional therapy, or surgery required after the active treatment phase of the trial is completed will be collected and recorded in the electronic case report form (eCRF) throughout all follow up visits until 12 months (±28 days) following the last RT treatment.

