#### 10.7 PROGRESSION-FREE SURVIVAL

The date that a patient's cancer progress, defined by a diagnosed with a new cancer, recurrent cancer or initiates more chemotherapy, will be collected on a monthly basis. Progression-free survival will be calculated from the time of enrollment to the earliest of date of cancer progression, death, or 12 months. If a subject drops out, withdraws or is terminates participation study early for some other reason, the subject will be censored at the last know status. Kaplan-Meier progression free survival curves with be constructed for the treatment groups and the curves compared using a log-rank test.

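### Progression-free survival is defined two ways: the protocol counts partial response and stable disease as progression, and the SAP uses a different event with no link to RECIST Progressive Disease

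*Protocol*

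**What the plan says.** Protocol 5.3 lists the objective: "To assess the impact of SGX942 on progression free survival through 12 months". SAP 1.3 repeats it, and SAP 2.3 lists PFS as a safety endpoint.

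Protocol 11.1.7 runs PFS from randomization to the earliest of death, completion of the 12-month assessment, or this imaging event: "The patient had an imaging report of tumor progression (RECIST 1.1 evaluation of less than" complete response).

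Elsewhere the protocol treats progression as its own category. Table 9 (6.2.2) defines Progressive Disease for the target lesion as ">20% increase from smallest sum of longest diameter recorded since treatment started (best response"), and Table 11 has four overall outcomes: complete response, partial response, stable disease and progressive disease. Section 11.1.4 compares the percentage "categorized as having a 'complete tumor response' or 'partial tumor response' at 12 weeks and 12 months post-RT", so partial response is grouped with the favourable outcomes.

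SAP 10.7 runs PFS from enrollment to the earliest of cancer progression, death or 12 months, with progression "defined by a diagnosed with a new cancer, recurrent cancer or initiates more chemotherapy, will be collected on a monthly basis". The SAP reprints the RECIST tables (its Tables 3 to 5) and uses them in 10.4, but does not connect them to PFS.

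On precedence, protocol 12.1 says: "Complete details of analyses and relative order of importance of each analysis are more fully delineated in the Statistical Analysis Plan". The SAP introduction describes the SAP as a more detailed elaboration of analyses in the protocol.

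**The concern.** A patient whose tumour has shrunk enough to be a partial responder is a treatment success in protocol 11.1.4 and a progression event in 11.1.7. That rule mixes true progression with incomplete response.

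The SAP rule has a smaller gap. Recurrence or a new cancer found on a scan can count. Growth of residual disease that nobody labels recurrent, and that is managed with surgery or a non-chemotherapy treatment, need not. Yet the trial collects "details pertaining to recurrence of disease, additional therapy, or surgery required after the active treatment phase of the trial is completed" (SAP 2.4.2) and, at the monthly contacts, "Initiation of additional anti-cancer therapy" (protocol 6.3.10).

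PFS is one of the checks that the drug does not worsen tumour outcome. Non-progression events spread evenly across arms dilute a real difference; spread unevenly, they can create or hide one. Two live definitions also leave room to choose between results after unblinding.

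**Working it through.** **The two rules side by side**

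| Element | Protocol 11.1.7 | SAP 10.7 |
|---|---|---|
| Start | Randomization | Enrollment |
| Progression event | Imaging result below complete response | New cancer, recurrent cancer or more chemotherapy |
| Partial response or stable disease on a scan | Event, as written | Not an event by itself |
| RECIST Progressive Disease | Event | Not named |
| Ascertainment | Imaging (scans at 12 weeks and 12 months) | Monthly |
| Reaching 12 months | End point, not labelled as censoring | Same |
| Early exit | Censored if lost to follow-up | Censored for any early exit |

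Neither document states an event count or power for PFS, so there is no plan figure to reproduce.

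**How many patients could be affected.** Phase 2 complete response at 3 months (protocol Table 4) was 17/27 on placebo and 18/27 on 1.5 mg/kg.

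- Below complete response: 27 − 17 = 10/27 = 37% (exact 95% CI 19 to 58%) on placebo, and 27 − 18 = 9/27 = 33% (17 to 54%) on 1.5 mg/kg.
- Difference, active minus placebo: −4 points (Wald 95% CI −29 to +22).
- Pooled: 19/54 = 35%. If all 260 patients were scanned at 12 weeks, 260 × 19/54 ≈ 91 would meet the protocol's imaging event at that scan.
- The table does not split partial response, stable disease and progressive disease, so the number wrongly counted lies between 0 and about 91.

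At 12 months the same table gives 22/23 and 19/23 complete responses. The evaluable patients differ by visit, but this is compatible with some patients reaching complete response after the 3-month scan.

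**Effect on the comparison.** Assumptions: 130 per arm; exponential PFS; 12-week scan at study week 19 and end at week 59 (protocol Table 7); two-sided 5% log-rank test. Hazard ratios are active versus placebo, so 2.0 is harm. Placebo 12-month PFS *S* and the false-event shares *f* are assumed. A share *f* of patients still event-free at week 19 is given a false event then. Results are from 3,000 simulated trials per cell.

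A closed-form check uses:

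- event-free at 12 months: S′ = S(1 − f), with S(active) = S(placebo)^HR
- apparent HR ≈ ln S′(active) / ln S′(placebo)
- events D = 130 × [(1 − S′(placebo)) + (1 − S′(active))]
- power ≈ Φ(ln HR × √(D/4) − 1.96)

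At S = 80% and true HR 2.0:

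- f = 0: S′ = 0.80 and 0.64, D = 72.8, power 84% (simulated 84%).
- f = 20%: S′ = 0.64 and 0.512, apparent HR 1.50, D = 110.2, power 57% (simulated 57%).
- f = 35%: S′ = 0.52 and 0.416, apparent HR 1.34, D = 138.3, power 41% (simulated 43%).

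Simulated power under the protocol rule, equal shares, true HR 2.0:

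| Placebo PFS | f = 0 | f = 20% | f = 35% |
|---|---|---|---|
| 65% | 97% | 87% | 78% |
| 80% | 84% | 57% | 43% |
| 90% | 55% | 25% | 18% |

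Unequal shares at placebo PFS 80% (placebo vs active):

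| Shares | No true effect | Power at true HR 2.0 |
|---|---|---|
| 35% vs 45% | apparent HR 1.29; false harm signal in 24% of trials | 81% |
| 35% vs 25% | apparent HR 0.77; false benefit signal in 25% | 13% |
| 37% vs 33% (Phase 2 point estimates) | false benefit signal in about 6 to 8% | about 26 to 30% |

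The last row gives the range over separate runs.

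SAP rule, placebo PFS 80%, true HR 2.0: if 10%, 20% or 30% of true events are never captured, power goes from about 83% to 79%, 71% or 62%.

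**The case against.** **The parenthesis may only qualify a report of progression.** On this softer reading, a scan report must first state progression. That is possible, but the parenthesis is the only imaging criterion given, and it still conflicts with Tables 9 to 11. At best the text is ambiguous.

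**The SAP rule is the one likely to be run.** Protocol 12.1 defers to the SAP, and the SAP is later: it cites June 2020 guidance, while protocol Amendment 3 is dated September 2019. This stands, and it makes the protocol-rule figures less likely to materialise. But an elaboration that changes the event without saying so leaves both rules in force, and deferring to the SAP does not close the SAP's own gap.

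**The scenarios are partly invented.** This also stands. The 10-point imbalances have no support in Phase 2, and a 35% share assumes almost nobody below complete response had progressed, so it is close to an upper bound. With the Phase 2 split, false signals are rare, although power at HR 2.0 is still low. For the SAP rule, later death, recurrence or chemotherapy would still count, so many missed events would be delayed and not lost; the 10 to 30% range is an assumption.

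**The consequence is limited.** PFS is outside the primary test and the five-endpoint hierarchy, and has no decision rule. Response categories and mortality are analysed separately. All of this is correct, and it limits how serious the point is.

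**Conclusion.** The concern holds. As written, the protocol's imaging event includes partial response and stable disease, which contradicts its own RECIST tables and 11.1.4. The SAP uses a different event set that is not tied to Progressive Disease, and neither document says which governs. The start point and the early-exit censoring rule differ as well.

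The conflict rests on the text alone. Its numerical size rests on assumptions about placebo PFS, misclassified shares and missed events that the documents do not supply, and the direction of any bias is not established. The point should be fixed because PFS is a named safety objective, but it does not threaten the primary efficacy conclusion.

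**What to change.** Put one definition in protocol 11.1.7 and SAP 10.7: time from randomization to the first of RECIST 1.1 overall Progressive Disease (protocol Table 11, SAP Table 5), documented recurrence, or death from any cause. State that patients event-free at the 12-month assessment are censored then, and that lost patients are censored at their last assessment. State one rule for new anti-cancer therapy of any kind (not only chemotherapy) and one for second cancers, with the alternative as a sensitivity analysis. Report below-complete-response rates under tumour response (11.1.4), not as progression.

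The cost is wording in two sections. Scans, recurrence, additional therapy, surgery and vital status are already collected, and SAP 10.7 already has new cancers collected monthly. The protocol edit would need ethics approval under protocol Section 13. If no further amendment is planned, the minimum is a SAP revision before unblinding that adopts this definition and says explicitly that it supersedes 11.1.7.

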11.2. Safety Parameters

11.2.1 Adverse Experience (AE)

Any noxious or unintended event that occurs in association with the use of an investigational agent in humans, whether considered related to the investigational agent or not. This definition encompasses symptoms or signs reported by the subject or detected by the investigator or other competent observer, as well as medically important deviations from normality in the results of ancillary investigations. If present at time of first dose of study drug, such AEs must be recorded as part of the medical history.

Treatment-Emergent Adverse Experience: An AE that is new in onset or aggravated in severity or frequency following entry into the study. In addition, any pathological finding on physical examination or diagnostic procedure that is new in occurrence or exacerbated in comparison with the subject's status at study entry is considered a treatment-emergent AE if it requires any medical or surgical intervention whatsoever (including, but not limited to, additional diagnostic procedures or alteration of prescribed therapy).

All AEs, whether judged to be related or not to the study drug, should be recorded in both the medical record and the eCRF. The start and resolution dates, the judgment of the severity of the AE, the judgment of the relationship of the AE to the study drug, the action taken for subsequent dose of study drug, and the outcome should be noted.

11.2.2 Serious Adverse Experience (SAE)

Any AE occurring at any dose that results in any of the following outcomes:

- Death
- A life-threatening AE
- Prolongation of existing hospitalization or subsequent need for hospitalization
- A persistent or significant disability/incapacity
- A congenital anomaly/birth defect
- A medical or surgical intervention to prevent one of the above

11.3. Relationship to Study Drug

The relationship of an AE to the assigned study drug is assessed using the following definitions:

Not Related: The drug experience is clearly related to other factors such as the patient's/subject's clinical state, therapeutic interventions, or concomitant drugs.

Original: 11 January 2017 Confidential

Possibly Related: The drug experience follows a reasonable sequence from the time of drug administration and/or follows a known response pattern to the study drug, but could have been produced by other factors such as the patient's/subject's clinical state, therapeutic interventions, or concomitant drugs.

Related: The drug experience follows a reasonable temporal sequence from the time of drug administration, follows a known response pattern to the study drug, and cannot be reasonably explained by other factors such as the patient's/subject's clinical state, therapeutic interventions, or concomitant drugs.

11.4. Severity of Adverse Event

A clinical determination of the intensity of an AE should be done for all reported AEs. The severity assessment should use the CTCAE grading system that assesses the severity of each AE from grades 1-5. The grading system can be found in Appendix 1.

11.5. Reporting Adverse Events

11.5.1 Adverse Events

All AEs that occur after any patient/subject has been enrolled, before treatment, during treatment, or within 6 weeks (± 4 days) following the cessation of RT treatment, whether or not they are related to the study, must be recorded in the eCRF. All AEs should be noted in the eCRF within 3 days of being recognized. Any adverse event that is either a SAE or potential SAE should be handled within the timeframes given in section 11.5.2, below. Each treatment-emergent AE should be reported spontaneously or in response to general, non-directed discussion with the attending nurse or physician (e.g., has there been any change in subject status since the last assessment period?). For each treatment-emergent AE, the investigator should obtain all the information required to complete the AE page of the case report form, in accordance with the guidelines that accompany it.

All treatment-emergent AEs, regardless of seriousness, severity, or presumed relationship to study therapy, must be recorded using medical terminology consistent with the source document and on the AE page. Whenever possible, diagnoses should be given when signs and symptoms are due to a common etiology. Investigators must record their opinion concerning the relationship of the AE to study therapy on the AE page.

All treatment-emergent AEs must be followed until resolution or until the 6-month follow up visit. All measures required for AE management and the ultimate outcome of the AE must be recorded in the source document and reported on the AE page. The resolution date for all recorded AEs should be entered within 3 days of determination that the AE has resolved.

11.5.2 Serious Adverse Events

All SAEs that occur after any patient/subject has been enrolled, before treatment, during treatment, or within six weeks (±4 days) following the last RT, whether or not they are related to the study, must be recorded on forms provided in the eCRF.

When the investigator, or trained designee, becomes aware that a serious or potentially serious AE (as defined above) has occurred, the site monitor or Medical Monitor must be notified

Original: 11 January 2017 Confidential Page 54 of 67

immediately (and no later than 24 hours after notification) by telephone, regardless of the relationship (or lack thereof) of the AE to study therapy.

All reports of serious or potentially serious AEs must be followed within 24 hours (or sooner at the request of the Soligenix Medical Monitor) by the completion of a serious AE form signed by the investigator. This should be emailed (or faxed if email impractical) to the site monitor *and* Medical Monitor.

In accordance with Soligenix SOPs and Health Authority regulations, investigators may be notified from time to time of the occurrence of serious, unexpected AEs. If such AEs are associated with the use of the study drug (i.e., there is a reasonable possibility that the AE may have been caused by the drug) and are thus deemed significant new adverse experiences or risks with respect to the drug, the investigator must promptly inform the relevant IRB/EC, in accordance with the ICH Guidance on GCPs (E6, April 1996).

FOR ADVERSE EXPERIENCE REPORTING OR MEDICAL QUESTIONS THE MEDICAL MONITOR SHOULD BE CONTACTED:

[name], Senior Vice President & Chief Medical Officer, Study Medical Monitor [contact] x 30

Email: [contact]

If above contact is not accessible, please call:

Soligenix, Inc., [name] [contact]

FOR ADDITIONAL ASSISTANCE:

For additional assistance, please contact your clinical research monitor(s) OR

[name], Clinical Research Manager

Office: [contact] x 23

Email: [contact]

